### **Aim 1: Investigate sex differences in the effect of exogenous PRO compared to placebo on impulsivity and smoking cessation**

Hypothesis 1: For both males and females, a lower proportion of subjects randomized to PRO will relapse by 4 weeks after quit date compared to those randomized to PBO.

Hypothesis 2: For both males and females, subjects randomized to PRO will have more days to relapse compared to those randomized to PBO.

Hypothesis 3: There will be a sex difference in smoking relapse such that females, regardless of randomization assignment, will have fewer days to relapse compared to males.

Hypothesis 4: Impulsivity will be a stronger relapse predictor in females than males.

Hypothesis 5: Among those with higher levels of serum PRO the influence of impulsivity on smoking relapse will be dampened.

Given that less than three percent of those who attempt to quit smoking remain abstinent six months later (Benowitz, 2009), there is an urgent need to gain a better understanding of the dynamic process involved in smoking cessation. This project will provide new knowledge regarding the possible protective role of progesterone against smoking relapse in males and females.

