#### B.4.7. Sample Size & Power Analysis

We expect an approximate drop-out rate of 25% based on our current, more burdensome protocol within a sample of 18-40 year-old females. Therefore, we will enroll a total of 125 female and 125 male participants to ensure we have 100 per sex group to complete the 4 week follow-up for the primary outcome. Participants will be randomized 1:1 to PRO or placebo, separately by sex group, as described above. In our earlier work ([name] et al, 2008), the luteal quit group had a prevalence of 66% relapse at 30 days; this estimates the placebo group relapse rate for our proposed study. Based on a two-tailed Pearson chi-square test with alpha=0.025 for each sex group, a sample size of 100 completers per sex group will have 80% power to detect an odds ratio of 3.5 or higher for comparing smoking relapse prevalence in the placebo group to smoking relapse prevalence in the PRO group. We observed an odds ratio of 3.2 for follicular quit group relapse compared to luteal quit group relapse ([name] et al, 2008). Since our PRO group will receive substantially more progesterone than the typical natural female cycle, it is reasonable to expect a slightly larger odds ratio for PRO compared to placebo. Since the difference in progesterone levels between the male PRO group and the male PBO group will be larger than the difference between the female PRO group and the female PBO group (see Figure 5), we expect a larger odds ratio (hence higher power) for the male treatment comparison.

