Safety analyses: Adverse events will be quantified separately by sex and treatment groups and compared across treatment groups with Fisher's exact test (for binary events) or with chi-square test (for counts of events or event rates).

Secondary outcome analyses: These address Hypothesis 2. Our secondary outcomes include the binary indicator of relapsed yes/no at the week 12 visit, and days to relapse, as described above. The binary outcome will be analyzed as described for the primary outcome. Days to relapse will be analyzed using Kaplan-Meier

curves with a log-rank test comparing treatments (unadjusted) and Cox proportional hazards analysis (adjusted for other characteristics), both of which allow for loss-to-follow up via right censoring (Therneau and Grambsch, 2000), separately for the CA and PA definitions. Adjusting variables will be selected as described for the primary outcome. The proportional hazards assumption on the treatment effect will be examined and tested (Lin, Wei, and Ying, 1993; Grambsch and Therneau, 1994).

Other analyses: To address Hypothesis 3, we will pool the male and female data and test for an interaction between sex and treatment assignment in an adjusted Cox regression for the days to relapse outcomes. To address Hypothesis 4, we will test a baseline impulsivity by sex interaction in the logistic regressions for the binary outcomes and in the Cox regressions for the days to relapse outcomes. To address Hypothesis 5, we will test a baseline impulsivity by baseline serum progesterone interaction in the logistic regressions for the binary outcomes and in the Cox regressions for the days to relapse outcomes. While this study was designed to be powered for Hypothesis 1, rather than for these comparisons, these will be used to generate preliminary data and hypotheses for future research on sex differences in addiction treatment and impulsivity.

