**Data Analysis Plan.** Addressing Hypothesis 1: Our primary outcome is the binary indicator of relapsed yes/no at the week 4 visit. An unadjusted assessment of the treatment effect will come from a logistic regression of this binary outcome on randomized treatment assignment, separately by sex. The sex-specific treatment effect will be considered statistically significant if the p-value is <0.025. All persons randomized and with a measured primary outcome at the week 4 visit will be included in this analysis, regardless of whether or not they ever took any of their assigned treatment (intent-to-treat analysis); persons with missed visits are discussed below. While we expect baseline covariates to be balanced across treatment groups due to the randomization, an adjusted assessment of the treatment effect will then be carried out by a logistic regression including the randomized treatment assignment and pre-specified adjusting covariates such as age, baseline progesterone, estradiol, baseline impulsivity measures, etc. This pre-specified list will be determined by the study team during the finalization of the protocol, prior to the first study enrollment. We expect these analyses to be somewhat conservative, since they do not explicitly account for the randomized permuted blocking (Matts and Lachin, 1988). An analysis that accounts for the blocking (such as a stratified Mantel-Haenzel test) cannot be generalized to include the adjustment for impulsivity measures, for example, which are a focus of this proposal.

Hypotheses:

Hypothesis 1: For both males and females, a lower proportion of subjects randomized to PRO will relapse by 4 weeks after quit date compared to those randomized to PBO.

Hypothesis 2: For both males and females, subjects randomized to PRO will have more days to relapse compared to those randomized to PBO.

Hypothesis 3: There will be a sex difference in smoking relapse such that females, regardless of randomization assignment, will have fewer days to relapse compared to males.

Hypothesis 4: Impulsivity will be a stronger relapse predictor in females than males.

Hypothesis 5: Among those with higher levels of serum PRO the influence of impulsivity on smoking relapse will be damped.

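### Hypothesis 3 is a difference between the sexes across both arms, but the only test named for it is the sex-by-treatment interaction

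*Combined protocol and SAP*

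**What the plan says.** Section A (Aim 1) states Hypothesis 3 as "females, regardless of randomization assignment, will have fewer days to relapse compared to males". The DSMP, section C, repeats it: "There will be a sex difference in smoking relapse such that females, regardless of randomization assignment".

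The analysis is in B.4.8 under Other analyses, and again in DSMP section C: "To address Hypothesis 3, we will pool the male and female data and test for an interaction between sex and treatment assignment". The model is an adjusted Cox regression for days to relapse. Covariates follow the earlier rule, "Adjusting variables will be selected as described for the primary outcome", and dropouts are censored, the log-rank and Cox methods being described as "both of which allow for loss-to-follow up via right censoring".

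The heading of Aim 1 asks a different question from Hypothesis 3: "Investigate sex differences in the effect of exogenous PRO compared to placebo on impulsivity and smoking cessation". On the status of Hypotheses 3 to 5, B.4.8 adds: "While this study was designed to be powered for Hypothesis 1, rather than for these comparisons". They are to supply preliminary data and ideas for later research.

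**The concern.** A difference between females and males whatever the arm is a main effect. A sex-by-treatment interaction is the difference between two treatment effects. The two can be present or absent independently.

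If females relapse sooner by the same factor in both arms, as Hypothesis 3 predicts, the interaction is zero and the planned test has no power beyond its error rate. If the interaction is significant, that does not establish Hypothesis 3, because it can arise with no average sex difference or with a sex difference in one arm only.

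The second risk is not remote. B.4.7 expects a larger treatment odds ratio in males than in females, which on that scale is itself a sex-by-treatment interaction. A significant result could then be read as support for Hypothesis 3 when it reflects a stronger progesterone effect in males. The plan does not say how either result would be interpreted.

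**Working it through.** **Is the sex effect tested anywhere else?** No.
- Hypothesis 1: logistic regression within each sex.
- Hypothesis 2: the log-rank test compares treatments.
- Hypothesis 4: impulsivity by sex.
- Hypothesis 5: impulsivity by progesterone.

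**What the planned test measures.** Code female = 1 and PRO = 1, and write the log hazard as b1·sex + b2·treatment + b3·sex·treatment.
- The sex log hazard ratio (HR) is b1 on placebo and b1 + b3 on PRO. Its average over arms is b1 + b3/2.
- Hypothesis 3 concerns that average, or both arm-specific values.
- The planned test is of b3 = 0. Equal sex effects in both arms give b3 = 0 whatever the size of b1.
- b1 in this model is the sex effect in the placebo arm only.

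**The plan's own power figure.** It concerns Hypothesis 1 only; none is given for Hypothesis 3. The placebo odds are 0.66/0.34 = 1.941. Dividing by 3.5 gives 0.555, so the PRO relapse rate is 0.555/1.555 = 0.357. With 50 per arm and two-sided alpha 0.025, power is 79.7%, which reproduces the stated 80%.

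**Inputs for the illustration.**
- From the documents: B.4.7 says "we will enroll a total of 125 female and 125 male participants to ensure we have 100 per sex group". With 1:1 allocation that is 125/2, about 62 per cell. The 66% relapse at 30 days is from B.4.7, and 84 days is the 12-week final visit in Table 1.
- Assumed: female:male HR 1.5 in both arms; PRO HR 1.0 or 0.6; two-sided 5%; exponential relapse times; the loss patterns below; no covariates. Relapse levels are the average of the two sexes on placebo.

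Rejection rates over 2,000 simulated trials (PRO HR 1.0 / 0.6):

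| Setting | Relapses | Sex term, no interaction | Planned interaction | b1 with interaction in model |
|---|---|---|---|---|
| (a) 75% by day 84 (assumed), 25% loss over 84 days | 167 / 146 | 75.0 / 68.0% | 4.8 / 4.7% | 45.8 / 46.0% |
| (b) 66% at 30 days, 25% loss over 84 days | 217 / 202 | 84.6 / 81.0% | 4.6 / 5.0% | 56.4 / 56.0% |
| (c) 66% at 30 days, 20% lost by day 28 | 197 / 181 | 81.0 / 77.8% | 4.6 / 4.7% | 51.9 / 51.1% |
| (d) 66% at 30 days, no loss | 235 / 221 | 86.6 / 85.0% | 4.9 / 5.4% | 61.0 / 60.8% |

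**Other sex hazard ratios** (PRO HR 1.0, a to d). At HR 1.3 the sex term rejects in 39.5, 48.2, 44.8 and 52.8% of trials. At HR 1.7 it rejects in 93.0, 97.0, 95.8 and 98.0%. The interaction stays at 4.1-5.2%.

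**Formula check.** Schoenfeld power for the sex term is Φ(√D/2 · ln HR − 1.96), with D relapses. At HR 1.5, ln HR = 0.405. D = 147 gives 69%, D = 184 gives 78.5% and D = 226 gives 86%, in line with the table.

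**Reverse case.** Take a sex HR of 1.5 on placebo and 1/1.5 = 0.67 on PRO, so the average log HR is zero. The interaction rejects in 67.9, 81.6 and 85.0% of trials (settings a, b, d), and the sex term in 6.6, 4.5 and 4.2%.

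**Smaller trial.** With 200 subjects, 90 days, PRO HR 0.6 and about 125 relapses, a sex HR of 1.5 in both arms gives 4% for the interaction and 64% for the sex term (1,000 trials). The reverse case there, with PRO HR 0.8, gives 60% and 8%. By formula, 100-150 relapses give the sex term 53-70% power at HR 1.5 and 26-36% at HR 1.3.

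**The case against.** The strongest reply has four parts.

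1. **The plan limits the consequence itself.** Hypothesis 3 is exploratory and no confirmatory decision hangs on it. This stands, and it caps the importance of the point.

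2. **The interaction bears on whether the sex effect holds in both arms, and one interaction fit yields both arm-specific sex hazard ratios.** This is partly right. But the test can only speak to equality between arms, not to whether a sex effect exists. It also does that weakly: with variance 16/D for the interaction log HR, power for a ratio of hazard ratios of 1.5 is 17-24% at 100-150 relapses. The arm-specific estimates would be available, but the plan does not name them.

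3. **The illustrations rest on assumptions, and the reverse case makes PRO work better in females, against B.4.7.** All the hazard ratios are assumed and the reverse case is hypothetical. Its direction is immaterial, however: swapping the sex labels makes PRO work better in males and, with equal cells and two-sided tests, leaves the rejection rates unchanged. Power is lower with 200 subjects, as shown above.

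4. **The sex term is not a clean test either.** If treatment effects differ by sex, it averages unequal arm-specific effects. Sex is not randomized, and B.4.3 places female quit dates in the luteal phase because that phase is thought favorable. These limits stand and belong beside the result. They do not make the interaction a test of Hypothesis 3.

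**Conclusion.** The concern holds. As written, the analysis answers a different question from Hypothesis 3: a null result is compatible with the hypothesis, and a significant one can occur when it is false. This follows from the model algebra and needs no assumed effect size.

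The size does depend on assumptions. At a common sex HR of 1.5, the planned test rejects in about 5% of trials, against 68-87% for the sex term with 250 enrolled, or 53-70% by formula at 100-150 relapses among 200. Reading b1 from the interaction model instead gives 46-61% with 250 enrolled, and for the placebo arm only.

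It should be fixed, but the reach is confined to one exploratory hypothesis. The primary analysis, sample size and safety analyses are unaffected.

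**What to change.** Make the same change in B.4.8 (Other analyses) and DSMP section C:

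1. Test Hypothesis 3 by the sex term in the pooled Cox model containing sex, treatment and the pre-specified covariates, without the interaction, for both the continuous and prolonged abstinence definitions. Report the hazard ratio with its confidence interval. Include age, because B.4.2 admits males to 60 but females only to 50.
2. Keep the sex-by-treatment interaction as a separate analysis of whether the progesterone effect differs by sex, under the Aim 1 heading. Report the sex hazard ratio in each arm beside it, so that an average over unequal effects is visible.
3. Report the sex hazard ratio with and without baseline progesterone and estradiol. B.4.8 lists both as possible covariates, both are expected to be related to sex, and the female baseline sample is timed to the LH surge (B.4.3). This is an advisable addition; the documents give no baseline hormone distribution from which to judge how much it matters.
4. State that the sex comparison is observational and that female quit dates are set by cycle phase.

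The cost is wording in two sections and one extra fit of a planned model. No new data are needed. Precision stays modest: if the true hazard ratio is near 1.3, power is 40-53% with 250 enrolled, and 26-36% with 100-150 relapses among 200.

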## **B. RESEARCH STRATEGY**

### **B.1. SIGNIFICANCE**

Cigarette smoking continues to be the number one cause of preventable morbidity and mortality in the United States (CDC, 2010). Compared to males, females are at an increased risk for development and maintenance of nicotine addiction (USDHHS, 2001). Preclinical and clinical studies have offered evidence to explain these observed sex differences, suggesting that sex hormones may modulate the reward system and related nicotine response (Lynch & Sofuoglu, 2010). Specifically, high levels of estrogen are associated with a heightened response to nicotine; whereas, high levels of progesterone are associated with a blunted response (Carroll & Anker, 2010; Lynch & Sofuoglu, 2010). Further, within the animal literature the administration of progesterone has been shown to be associated with reduced reinforcing effects of drugs, as well as a decrease in self-administration and drug-seeking behavior (Carroll & Anker, 2010).

Recent studies suggest that progesterone may play a key role in the observed sex differences in addictive behaviors. A review by Lynch & Sofuoglu (2010) concluded that progesterone (PRO) may counter the enhanced vulnerability in females by altering the biological response to nicotine's reinforcing effects. Other clinical research on smoking cessation by menstrual phase has indicated that the follicular phase (low PRO) may be associated with more favorable outcomes when paired with nicotine replacement therapy (Franklin et al 2007; Carpenter et al 2008); whereas the luteal phase (high PRO) may be associated with more favorable outcomes when either no medication or non-nicotine medications (i.e. bupropion) are used ([name] et al 2008; Mazure et al 2011). However, the specific mechanisms as to how PRO may assist with smoking cessation efforts remain unknown. Given that PRO has been shown to reduce impulsive behaviors in animals (Llaneza and Frye, 2009) one theory is that PRO blunts impulsivity in humans and, therefore, protects against smoking relapse.

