This project, especially in the context of the other projects, is highly significant in several domains. First, the proposed work directly compares female and male subjects with respect to PRO modulation of smoking cessation. Second, because PRO and impulsivity both have a role in smoking cessation and relapse, a direct comparison of PRO versus PBO on impulsivity is important. Third, these data will directly address (a) the role of PRO on smoking cessation outcomes, (b) the role of sex differences on smoking cessation outcomes, (c) the role of impulsivity on smoking cessation outcomes, and (d) interactions of sex, PRO and impulsivity on smoking cessation outcomes. Fourth, while Project I will focus solely on nicotine and PRO effects on nicotine, Project II, using similar design features, will focus on cocaine with co-morbid nicotine use in humans and the combined effects of PRO and atomoxetine. Project III will conduct parallel preclinical studies to both projects. Therefore, the complete data set will provide unique and significant insights into sex differences as well as, translational data. Finally, the combined expertise of the assembled named investigators is unique and greatly enhances the probability that the work will be completed as proposed and that significant findings will be forthcoming.

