impulsivity, personality characteristics, stress, caffeine use, smoking withdrawal and behavior will be completed. At the second screening visit (Screening Visit 2; scheduled within three days of the first screening visit), baseline impulsivity tasks will be completed. Females will then be provided with urine luteinizing hormone (LH) testing kits with instructions for daily use. The quit date will be set based on LH testing results (details below). The investigators will review the data to determine eligibility. Subjects meeting eligibility criteria will be given instructions on when to come back for their Baseline Visit (details below).

**Quit Date Assignment:** This procedure will be identical to Project II and is described in detail here (Table 1). For *female subjects* the quit date will be assigned during the luteal phase. We have selected the luteal phase (typically the last 14 days of the menstrual cycle; Yee et al 1999) for quit date given that our prior work has demonstrated that this menstrual phase is associated with improved smoking cessation outcomes ([name] et al 2008). Therefore, using identical techniques from our prior work ([name] et al 2008) the quit date will be set as follows: First, to determine date of ovulation, female subjects will use LH tests. Several studies by our group and others have shown that ovulation can accurately be predicted by urine LH testing (e.g. [name] et al 1999, [name] et al 2000, [name] et al 2008, Grinsted et al 1989, Luciano et al 1990). Using the First Response urine testing kit (Carter Products), subjects will determine their LH peak with daily urine testing during specific days of the cycle (See Appendix A for instructions). The testing will be done for ten consecutive days starting on Day 8-12 (depending on cycle length). Although the surge may last up to three days, the first day of the surge is most important, because it predicts ovulation 24-48 hours later. In our prior studies, as well as our current study, subjects found the test easy to use and have been compliant. If no LH surge is identified in the first two months, that female subject will be labeled anovulatory and dropped for ineligibility (estimated < 5% occurrence). Second, once ovulation is detected, the baseline appointment and quit date will be scheduled. The baseline appointment will occur within three days of ovulation. Quit date will be set for seven days after the baseline appointment (i.e. seven to ten days after ovulation).

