Since this entails a delay of variable duration from Screening Visit 2 to Baseline

Visit (thus impacting timing of medication initiation) across female subjects, each *male subject* will be matched to a female subject for a similar delay so that, across the male and female groups, study procedures will be follow a similar chronology.

**Baseline Visit (Visit 3):** When the LH surge occurs female subjects will be instructed to come into the clinic within three days for their baseline visit and to start medication. Male subjects will be instructed to come into the clinic according to their assigned delay (per list generated by the Biostatistics Core). This visit will occur seven days prior to quit date. At this visit, subjects will be randomized to PRO or PBO within strata defined by sex. The Statistical Analysis Core (SAC) will generate the randomization tables (one for each sex), and the Clinical Trials Research Pharmacy will use it to determine randomization assignment. Randomization assignment will be stored in a secure file in a secure location at the Clinical Trials Research Pharmacy, to be shared only with the SAC. All other project staff including PI and study coordinator, as well as the participant, will remain blinded to the randomization assignment.

At the baseline visit subjects will provide a blood sample (for hormone assessment), breath sample (to confirm smoking status via carbon monoxide breathalyzer), have their vital signs (blood pressure, heart rate, weight) measured, be informed of their quit date, and receive brief behavioral counseling to prepare for their quit date. At the end of this visit subjects will be paid for their time and given study medication along with instructions for taking the medication (beginning at 8PM that day), as well as a clinic visit schedule for the remaining clinic visits. This visit will take approximately one hour to complete.

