**Table 1. Timing of Study Procedures by Sex**

	Female Subjects	Male Subjects
Initial Phone Interview		Anytime
Screening Visit 1	Menstrual Cycle Days 1-7	Within 2 weeks of Phone Screen
Screening Visit 2		Within 3 days of Screening Visit 1
Baseline Visit	Within 3 days after LH Surge	Delay matched to Female Subject
Medication Start		8PM on day of Baseline Visit
Quit Date		7 days after Baseline Visit
Week 0		Day of Quit Date
Week 1-Week 11		Weekly
Medication End		Day of Week 11 Visit
Final Visit		12 Weeks after Quit Date

Weeks 0-12 (Visits 4-16): The Week 0 clinic visit will occur on the assigned quit date. Subjects will attend clinic visits on a weekly basis thereafter for twelve weeks. At weeks 0-4, week 8 and week 12 blood samples (hormone measurement) will be collected. Urine samples will be collected at all visits from all participants (pregnancy tests for females; and visual inspection of urine color to confirm compliance with taking study medication via riboflavin filler). At weeks 0-4, week 8 and week 12 urine will be saved for biochemical confirmation of smoking status via nicotine/cotinine levels. Subjects will also complete several forms and questionnaires (described below). Subjects will also return the medication bottle and unused medication, be given a new two-week supply and adverse events will be assessed. At Week 11, study medication will be discontinued. Finally, subjects will receive brief smoking cessation behavioral counseling (Appendix A). At the end of each visit subjects will be paid for their time. These visits will take approximately 30-45 minutes to complete.

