(6-14 ng/mL) since that phase has been shown to be favorable for smoking cessation ([name] et al 2008). We expect the following serum progesterone levels by group (Figure 5): (1) females + PRO 9-13 ng/mL; (2) males + PRO 6-7 ng/mL; (3) females + PBO, varies by menstrual phase from 1-14 ng/mL; and (4) males + PBO 0-1 ng/mL (Goletiani et al 2007; Reed et al 2010; Yen et al 1999). Delivery of exogenous progesterone has been successfully used in prior research with a shorter duration of use (i.e. < 1 month) and is generally well tolerated (Sofouglu et al 2001; Sofouglu, et al 2004; Goletaini et al 2007; Reed et al 2010). The most common adverse effect in males and females is sedation. Less common effects include breakthrough bleeding (females), nausea (females and males) and breast tenderness (females) (de Lignieres, 1999; Goletaini et al 2007). While it is possible that progestins may contribute to risk for thromboembolism, we will be using natural micronized progesterone instead of synthetic progestins. Natural micronized progesterone is not known to be associated with thromboembolic risk (PDR, 2002; Goletaini et al 2007), and consequently is a safer choice. Micronized progesterone is not a form of birth control. Therefore, all female subjects will be educated on the importance of using a double-barrier method to protect against pregnancy.

**Adverse Effects:** If a subject is unable to tolerate these side effects of the study medication, those subjects will have the dosage decreased to 200 mg daily. The blind will not be broken to make this determination. [name] will assess the adverse event based on subject self-report of symptoms and advise a dose reduction if needed.

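### Hypothesis 5 is tested only with progesterone drawn before the first dose, so no planned analysis asks whether the progesterone given in the trial dampens the effect of impulsivity on relapse

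*Combined protocol and SAP*

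**What the plan says.** - **The hypothesis.** Aim 1 concerns the effect of exogenous progesterone compared with placebo. Under it, Hypothesis 5 reads: "Among those with higher levels of serum PRO the influence of impulsivity on smoking relapse will be dampened". Section B.1 adds that the data will directly address "interactions of sex, PRO and impulsivity on smoking cessation outcomes".
- **The test.** B.4.8 (Other analyses) says "we will test a baseline impulsivity by baseline serum progesterone interaction in the logistic regressions for the binary outcomes", and the same term goes into the Cox models for days to relapse. Section C of the Data Safety and Monitoring Plan (Data Analysis Plan) repeats this and adds no alternative.
- **When baseline is.** B.4.3 places the baseline blood draw at Visit 3. For females, "The baseline appointment will occur within three days of ovulation". At the end of that visit subjects are "given study medication along with instructions for taking the medication (beginning at 8PM that day").
- **Later samples.** "At weeks 0-4, week 8 and week 12 blood samples (hormone measurement) will be collected". The only specific use stated for on-treatment progesterone is the compliance check in B.4.9. The Rules/Changes page at the end of the document sends baseline, week 4 and week 12 hormone samples for assay.
- **Expected levels.** B.4.5 expects 9-13 ng/mL for females on progesterone, and for the other groups "males + PRO 6-7 ng/mL; (3) females + PBO, varies by menstrual phase from 1-14 ng/mL; and (4) males + PBO 0-1 ng/mL".
- **Status.** B.4.8 says that the study is powered for Hypothesis 1. The analyses for Hypotheses 3 to 5 are meant to generate preliminary data and hypotheses.

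**The concern.** The hypothesis speaks of serum progesterone level in a trial that sets that level by randomization. The planned moderator is fixed before randomized treatment can act on it, so it differs between arms only by chance. The randomized contrast in progesterone, which is the reason for the trial, therefore plays no part in the test.

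The rationale in B.1 is that progesterone may protect against relapse by blunting impulsivity. If the Hypothesis 5 interaction comes out null, it could be reported as evidence against that mechanism although the drug was never examined for it. If it comes out positive, it could be credited to the drug when it concerns natural hormone level. Since these analyses are meant to steer later research, a misattributed exploratory result is the harm.

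**Working it through.** **Step 1: is any other planned analysis a test of dampening by the drug?** Every model term that involves arm, impulsivity or progesterone in B.4.8 and in the monitoring plan is listed here.

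- Randomized arm: main effect in the primary and secondary models, and one interaction, with sex (Hypothesis 3).
- Baseline impulsivity: adjusting covariate in the treatment models, and interactions with sex (Hypothesis 4) and with baseline progesterone (Hypothesis 5).
- Baseline progesterone: adjusting covariate, and the Hypothesis 5 interaction.
- On-treatment progesterone: no model term.

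An additive covariate does not test dampening. No impulsivity by arm term and no impulsivity by on-treatment progesterone term is planned.

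**Step 2: can baseline mean an on-treatment value?** Screening Visit 1 and the Baseline Visit both precede the 8PM first dose (B.4.3 and Table 1). On either reading baseline is pre-dose.

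**Step 3: how much of the progesterone contrast does this leave out?** Inputs are the B.4.5 ranges. Assumptions: uniform within each range, 1:1 arms. Between-arm variance is (difference in means / 2)². Within-arm variance is range²/12, averaged over the arms.

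- Males: means 6.5 and 0.5. Between = (6.0/2)² = 9.00. Within = 1²/12 = 0.08. Share due to arm = 9.00/9.08 = 99%.
- Females: means 11 and 7.5. Between = (3.5/2)² = 3.06. Within = (4²/12 + 13²/12)/2 = (1.33 + 14.08)/2 = 7.71. Share due to arm = 3.06/10.77 = 28%.

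The planned moderator carries none of the arm share. In males, taking the placebo range as the pre-dose range, it spans about 1 ng/mL against an arm difference of 6 ng/mL.

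**Step 4: what might that do to the tests?** The plan states no power for Hypothesis 5, so there is no figure to reproduce. (The 80% for Hypothesis 1 does reproduce, at 79.7% with 50 per arm, 66% against 35.7% relapse and two-sided alpha 0.025, but it has no bearing here.) The following is illustrative only.

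Assumed model: logit P(relapse) = logit(0.66) + (b0 − slope × on-treatment progesterone) × impulsivity, with impulsivity standard normal, n = 100 per sex, two-sided 0.05. Rejections are counted in the direction of Hypothesis 5, where chance is 2.5%. The slope is 0.12 per ng/mL.

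| Group | Planned test, baseline unrelated to later level | Planned test, correlation 0.8 | Arm test |
|---|---|---|---|
| Males, b0 = 0.9 | 2.4% | 3.2% | 33% |
| Females, b0 = 0.9 | 2.4% | 16.0% | 15-16% |
| Females, b0 = 1.7 | 2.2% | 13.7% | 11-12% |

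The arm difference in the impulsivity log odds ratio is 0.12 × 6.0 = 0.72 in males and 0.12 × 3.5 = 0.42 in females, which is why the arm test is weaker in females. The documents give no effect size and no correlation between baseline and later progesterone.

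**Step 5: how many tests would the missing term add?** B.4.6 lists five composite impulsivity domains built around seven instruments. There are four relapse outcomes: point prevalence at weeks 4 and 12, and days to relapse by the continuous and prolonged definitions. Five domains × 4 outcomes = 20 tests pooled, or 40 by sex. Seven instruments × 4 × 2 sexes = 56. One named measure gives 4 pooled or 8 by sex.

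**The case against.** The strongest defence is that the planned choice is deliberate and safe. A pre-randomization moderator is not distorted by adherence or by anything that follows relapse. The documents also use the same abbreviation for natural hormone, as where B.1 says "the luteal phase (high PRO) may be associated with more favorable outcomes", so Hypothesis 5 could be meant as a statement about natural level. B.4.8 names the variable as baseline, so a careful reader would not take a null as a result about the drug. The analysis is exploratory, and the data for an arm interaction are kept and could be used later.

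Much of this stands. The planned test is a legitimate answer to a narrower question and should be kept. But the natural-level reading is nowhere stated, it leaves the interaction promised in B.1 without a test, and it gives males almost no variation to work with. An arm interaction added after the results are known would be post hoc.

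Three stronger readings are tempting and are not supported:

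- *That the trial's main result is at risk.* It is not. Hypothesis 1 does not depend on this term.
- *That Hypothesis 4, if true, would produce a spurious Hypothesis 5 result.* This needs a pooled model without impulsivity by sex. The plan never states such a model: the primary models are run by sex, and impulsivity by sex is already planned for Hypothesis 4.
- *That the arm test is clearly more powerful throughout.* In females it is not, if baseline tracks later levels. Whether arm or on-treatment level makes the better moderator depends on the assumed mechanism, so simulation cannot rank the two.

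**Conclusion.** The gap is established by the text alone. The one analysis assigned to Hypothesis 5 uses a value independent of arm, and no planned term asks whether administered progesterone changes the impulsivity effect. In males the planned moderator has almost no range. In females it addresses only natural progesterone around ovulation, and how far that predicts later levels is not given. The variance shares of 99% and 28% rest on the protocol's expected ranges and on uniform spread within them. The rejection rates rest on assumed effects and correlations and serve only as illustration. Severity is modest, because the hypothesis is declared exploratory and unpowered. The change is still worth making, because it is cheap and lets the trial address the question that its aim poses.

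**What to change.** 1. Add a baseline impulsivity by randomized arm interaction for the relapse outcomes, as the randomized exploratory test of dampening by administered progesterone. Run it by sex, or pooled with sex and impulsivity by sex in the model, and say which. State that it tests assignment, not serum level, and that it is low-powered, especially in females.
2. Keep the baseline-progesterone interaction, by sex or with impulsivity by sex in the model, labelled as a test of natural pre-treatment level only.
3. Name one lead impulsivity measure or composite for these tests.

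Any analysis of on-treatment progesterone is optional. It should be labelled observational and limited to outcomes that occur after the sample was drawn.

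The cost of items 1 to 3 is SAP wording and a few more exploratory tests: 4 pooled or 8 by sex for the new term with one named measure, against 20 or 40 across the five domains. No new samples, assays or visits are needed.
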